Data from KCP-330-003, a food effect study in patients with sarcomas (NCT01896505) has shown a 15% increased exposure to selinexor when patients take the medication with food, regardless of fat content, versus the fasting state.

Several correlative biological studies have been initiated as part of the phase 1 trial, including study of XPO1 levels in peripheral white blood cells pre- and post-treatment. In addition, the KING trial includes a surgical arm allowing study of resected tumors after up to three doses of selinexor. This has included administration of the medication on the morning of surgery with a sip of water, up to two hours before induction of anesthesia. Patients have then been allowed to resume oral selinexor after recovery (1 to 5 weeks after surgery). There have been no adverse effects associated with this pre and post-operative administration of selinexor, including on wound healing (personal communication, [name]). Studies on this tissue included measurement of intra-tumoral drug levels, as well as other assays examining pharmacodynamic effect of selinexor on tumor cells, including induction of apoptosis, and XPO1 mRNA and protein levels. Preliminary data from 7 patients showed that selinexor reached therapeutic concentrations of ~50-300 nM within brain tumor tissues, with a median plasma concentration of 122 nM in adult GBM after ~2 hours.

## 2.5 Pediatric Studies

### 2.5.1 Prior Experience in Children (Updated with amendment 4):

In a pediatric Phase 1 trial of selinexor in children with recurrent/progressive leukemia run through the Dana-Farber Leukemia Consortium (DFCI), the recommended Phase 2 dose was determined to be 40 mg/m^2 twice weekly, 8 doses in a 28 day cycle. Two DLTs were encountered: pancreatitis (30 mg/m^2) and cognitive disturbance (56 mg/m^2). Single agent activity was noted with an ORR of 12.5% [1 CRp (AML), 1 PR (ALL)] and 2 of 4 patients with ALL experienced Grade 4 tumor lysis syndrome. In addition, as part of a St. Jude Hospital investigator sponsored trial evaluating selinexor (Days 1, 3, 8, 10, 22, and 24) with fludarabine and cytarabine (Days 15 through 19) for treatment of refractory or relapsed leukemia or myelodysplastic syndrome, the MTD of selinexor was 55 mg/m^2. The dose-limiting toxicity at 70 mg/m^2 was reversible cerebellar toxicity, but at and above 40 mg/m^2, all patients treated demonstrated evidence of XPO1 target inhibition.

### 2.5.2 Pharmacology/Pharmacokinetics/Correlative Biological Studies

The below table depicts pharmacokinetic results obtained from four pediatric patients dosed at 30 mg/m^2 twice weekly with selinexor. The data shows that pharmacokinetic parameters observed in pediatric patients (n=4) at 30 mg/m^2 are comparable to those observed in adult patients administered with the same selinexor dose.

	Cmax (ng/mL)	AUC0-8 (ng*h/mL)	AUCinf (ng*h/mL)	Tmax (h)	T½ (h)	Vd/F (mL)
Pediatric Patients						
Day 1	569	1893	4180	2.75	6.55	1866
Day 22a	425	1854	NC	2.67	NC	NC
Adult Patients						
Day 1	443	1959	3040	2.0	5.2	2078
Day 17	378	1849	NC	2.0	NC	NC

NC = not calculable

a One patient collected on Day 15

(Amendment 4) The updated pharmacokinetic data from the DFCI trial continue to demonstrate that the pharmacokinetics of selinexor in children are dose proportional and achieve exposures similar or slightly higher than that of adults. (Place et al ASH 2018).

## 2.6 Overview of Proposed Pediatric Study

We will conduct a phase 1 trial of selinexor in children with recurrent or refractory solid tumors, including CNS tumors using the Rolling Six design. The aims of the trial will be to establish the maximum tolerated pediatric doses of tablet formulation; to investigate the toxicities, pharmacokinetics, and pharmacodynamics of selinexor in children with cancer; and to preliminarily explore efficacy in pediatric solid and CNS tumors, including medical and surgical expansion cohorts of HGG patients.

After the recommended Phase 2 dose has been determined on the dose-escalation portion Part A, Parts B and C will open concurrently. During the initial cohort, patients received selinexor twice weekly (once on each day) on a days 1,3 schedule (Mon/Wed,Tue/Thurs, or Wed/Fri). One cycle was 28 days or 8 doses. Due to unanticipated hematological toxicity the schedule was revised (Amendment #1 April 2016) and subsequent patients received selinexor twice weekly (once on each day) on a days 1,3 schedule (Mon/Wed,Tue/Thurs, or Wed/Fri) during weeks 1-3, followed by a 7 day break. One cycle was 28 days or 6 doses. With Amendment #4, given evidence from adult trials showing equivalent efficacy of once and twice weekly dosing with increased tolerability when given once weekly, the once weekly dosing schedule will be tested. Each 28 day cycle will consist of selinexor given once a week for 4 doses.

Toxicity will be assessed using CTCAE v5.0. Imaging for disease evaluation during the dose escalation phase will occur at the end of Cycle 1, every other cycle x 2, and every 3 cycles thereafter. Disease response will be assessed according to RECIST v1.1 criteria for solid tumors and 2-dimensional measurement for CNS tumors.

## 2.8 Rationale for Change in Dosing Schedule (Amendment #4)

Over 2,601 patients have received selinexor to date through numerous clinical trials for a variety of malignancies, both as a single agent and in combination. Despite the MTD determination of 65 mg/m^2/dose in adult single agent Phase 1 studies on the twice weekly (8 dose/ cycle) schedule, most studies are now using reduced doses of 35-45 mg/m^2/dose due to analysis of safety and pharmacokinetic data showing acceptable efficacy and improved long-term tolerability. The most recent FDA approval for multiple myeloma uses selinexor in combination with dexamethasone at the equivalent of 45 mg/m^2/dose (80mg flat dosing). Furthermore, it is clear from multiple adult trials of selinexor that weekly dosing, even at higher individual doses, reduces myelosuppression and neurotoxicity compared to twice weekly dosing. Positive results have been presented in patients with sarcoma, acute myeloid leukemia, diffuse large B cell lymphoma, and others.

In the Phase 2 trial of selinexor in recurrent glioblastoma (the KING trial), investigators have reported results showing a 30% 6 cycle PFS rate and a 10% overall response rate using the flat 80 mg weekly schedule (equivalent to 45 mg/m^2). No Grade 3 or 4 non-hematologic adverse events were reported using this dose and schedule which was the regimen that was most effective and best tolerated; out of 30 subjects, there were no non-hematologic Grade 3/4 events, Grade 3 neutropenia developed in 3 patients, and Grade 3 leukopenia, Grade 3 lymphopenia, and Grade 4 lymphopenia developed in 1 patient each.

THIS PROTOCOL IS FOR RESEARCH PURPOSES ONLY, SEE PAGE 1 FOR USAGE POLICY

Investigators also demonstrated average intratumoral drug levels of 122 nM, on par with the *in vitro* IC50 described in the preclinical studies in adult and pediatric HGG.

Comparative pharmacokinetic (PK) analysis between ADVL1414 and multiple adult studies suggest Cmax and AUC values at 20 mg/m^2 were similar to those seen at 35 mg/m^2 dosing in adults, and values at 35 mg/m^2 compared favorably to those seen at doses up to 60 mg/m^2 in adults. 35 mg/m^2 dosing in children would therefore appear to produce at least equivalent PK values to the 80 mg flat dosing that produced the best responses in the KING trial, even when given weekly. A dose of 20 mg/m^2, on the other hand, is unlikely to produce adequate exposure for CNS tumor response, based on available clinical and preclinical data. Since progress in the trial to this point has demonstrated 20 mg/m^2 twice weekly (40 mg/m^2 cumulative per week) to be tolerable, we will use 45 mg/m^2 (a 12.5% increase in dose intensity) as our starting dose on the once weekly schedule which is anticipated to be less toxic than twice weekly dosing. We will have one dose escalation to 55 mg/m^2 and one available de-escalation to 35 mg/m^2, the lowest dose considered likely to produce adequate CNS exposure to be efficacious based on available evidence. We hypothesize that tolerability will be improved, that the RP2D for weekly dosing will be higher than the current RP2D for twice weekly dosing, and that Cmax and AUC values equivalent or higher will be achieved and compare favorably to the dosing levels in adults at which responses have been observed.

Table A:

		Dose (mg/m  )	T max (hr)	C max (ng/ml)	t 1/2 (hrs)	AUC (hr*ng/ml)	C 1/F (L/hr/m  )
ADVL1414	Solid Tumors; Tablet with food Schedule- Days 1, 3, 8, 10, 15, 17, [22, 24]; PK- T= 0, 0.5, 1, 3, 4, 6, 8, 24 h	35, (n=19)	2 (0.5-6)	535 ± 174	7.9 ± 4.1	5156 ± 1227	7.12 ± 1.34
		20 (n=12)	4 (1-6)	324 ± 116	7.2 ± 1.2	3092 ± 842	6.98 ± 1.55
Alexander et al, 2016	Pediatric Acute Leukemia, No acetaminophen; Schedule- Days 1, 3, 8, 10, 22, and 24. PK- T=0, 0.5, 1, 2, 4, 8, 24, 48 h	30 + fludarabine (n=4)	3 ± 1.5	537 ± 281	6 ± 1	AUC 0-48h = 4,351 ± 513	
Abdul Razak et al, 2016	Adult Solid Tumors Schedules- Multiple; PK- T= 0, 0.5, 1, 2, 4, 8, 24, 48 h	20 (n=5)	4 ± 3	237 ± 105	6 ± 1	AUC 0-48h = 2,614 ± 603	
		35 (n=10)	4 ± 2	358 ± 82	7 ± 4	AUC 0-48h = 3,901 ± 932	
Gounder et al, 2016	Advanced Refractory Bone or Soft Tissue Sarcoma, Schedule- D1, D3 q Wx3 → 1 week off, Food Effect Study; PK- T= 0, 0.25, 0.5, 1, 1.5, 2, 3, 4, 5, 6, 8, 10, 24 h	30 (n=12); 1 st gen tab, low-fat meal	3.5 ± 1.7	448 ± 88	5.5 ± 1.0	3,647 ± 648	
		60 mg (n=12); fed, oral suspension	1.8 ± 2.5	482 ± 218	6.7 ± 1.6	4,048 ± 771	
Lassman et al, 2017 WFNOS 5th Quadrennial Meeting Zurich, Switzerland.	KPT-330 (selinexor) IN patients with recurrent Gliomas (KING)	50, B1W pre- and post-surgery		C 1hr = 836 nM (370 ng/ml) C 2hr = 967 nM (429 ng/ml)			

Values for Tmax are median (range); Values for all other results are mean (SD)

### 3.0 SCREENING AND STUDY ENROLLMENT PROCEDURES

Patient enrollment for this study will be facilitated using the Slot-Reservation System in conjunction with the Oncology Patient Enrollment Network (OPEN) a web-based registration

THIS PROTOCOL IS FOR RESEARCH PURPOSES ONLY, SEE PAGE 1 FOR USAGE POLICY

system available on a 24/7 basis. OPEN is integrated with CTSU regulatory and roster data and with the Lead Protocol Organization (LPOs) registration/randomization systems or Theradex Interactive Web Response System (IWRS) for retrieval of patient registration/randomization assignment. OPEN will populate the patient enrollment data in NCI's clinical data management system, Medidata Rave.

Requirements for OPEN access:

- A valid CTEP-IAM account;
- To perform enrollments or request slot reservations: Be on a LPO roster, ETCTN Corresponding roster, or PO roster with the role of Registrar. Registrars must hold a minimum of an AP registration type;
- If a Delegation of Tasks Log (DTL) is required for the study, the registrar(s) must hold the OPEN Registrar task on the DTL for the site; and
- Have an approved site registration for a protocol prior to patient enrollment.

To assign an Investigator (IVR) or Non-Physician Investigator (NPiVR) as the treating, crediting, consenting, drug shipment (IVR only), or receiving investigator for a patient transfer in OPEN, the IVR or NPiVR must list the IRB number used on the site's IRB approval on their Form FDA 1572 in RCR. If a DTL is required for the study, the IVR or NPiVR must be assigned the appropriate OPEN-related tasks on the DTL.

Prior to accessing OPEN, site staff should verify the following:

- Patient has met all eligibility criteria within the protocol stated timeframes; and
- All patients have signed an appropriate consent form and HIPAA authorization form (if applicable).

Note: The OPEN system will provide the site with a printable confirmation of registration and treatment information. You may print this confirmation for your records.

Access OPEN at <https://open.ctsu.org> or from the OPEN link on the CTSU members' website. Further instructional information is in the OPEN section of the CTSU website at <https://www.ctsu.org> or <https://open.ctsu.org>. For any additional questions, contact the CTSU Help Desk at [name] or [[contact]](mailto:[contact]).

### 3.1 Current Study Status

Investigators should refer to the COG website to determine if the study is currently open for accrual. If the study is listed as active, investigators should then access the Studies Requiring Reservations page to ensure that a reservation for the study is available. To access the Studies Requiring Reservations page:

1. Log in to <https://open.ctsu.org/open/>
2. Click the **Slot Reservation** Tab. *The Site Patient page opens.*
3. Click the **Report** Tab. *The Slot Reservation Report opens. Available Slots are detailed per study strata.*

### 3.2 IRB Approval

Local IRB approval of this study must be obtained by a site prior to enrolling patients. Sites must submit IRB approvals to the NCI's Cancer Trials Support Unit (CTSUSU) Regulatory Office and allow 3 business days for processing. The CTSUSU IRB Certification Form may be submitted in lieu of the signed IRB approval letter. All CTSUSU forms can be located on the CTSUSU web page ([www.ctsu.org](http://www.ctsu.org)). Any other regulatory documents needed for access to the study enrollment screens will be listed for the study on the CTSUSU Member's Website under the Regulatory Tab.

Sites participating on the NCI CIRB initiative and accepting CIRB approval for the study

THIS PROTOCOL IS FOR RESEARCH PURPOSES ONLY, SEE PAGE 1 FOR USAGE POLICY

are not required to submit separate IRB approval documentation to the CTSU Regulatory Office for initial, continuing or amendment review. This information will be provided to the CTSU Regulatory Office from the CIRB at the time the site's Signatory Institution accepts the CIRB approval. The Signatory site may be contacted by the CTSU Regulatory Office or asked to complete information verifying the participating institutions on the study.

#### **Submitting Regulatory Documents:**

Submit required forms and documents to the CTSU Regulatory Office using the Regulatory Submission Portal on the CTSU website.

To access the Regulatory Submission Portal log in to the CTSU members' website, go to the Regulatory section and select Regulatory Submission.

Institutions with patients waiting that are unable to use the Regulatory Submission Portal should alert the CTSU Regulatory Office immediately at [name] in order to receive further instruction and support.

### **3.3 Patient Registration in the COG Registry**

Prior to enrollment on study, patients must be assigned a COG patient ID number. This number is obtained via the COG Registry system once authorization for the release of protected health information (PHI) has been obtained.

### **3.4 Reservation and Contact Requirements**

Once a slot-reservation confirmation is obtained after making a reservation in OPEN, the Study Chair or Vice Chair should be notified and site staff may then proceed to enroll patients to this study. (The patient will need a COG patient ID number in order to obtain a reservation). Patients must be enrolled within 7 calendar days of making a reservation.

Reservations may be obtained 24-hours a day through the OPEN website.

### **3.5 Informed Consent/Assent**

The investigational nature and objectives of the trial, the procedures and treatments involved and their attendant risks and discomforts, and potential alternative therapies will be carefully explained to the patient or the patient's parents or guardian if the patient is a child, and a signed informed consent and assent will be obtained according to institutional guidelines.

### **3.6 Screening Procedures**

Diagnostic or laboratory studies performed exclusively to determine eligibility for this trial must only be done after obtaining written informed consent. This can be accomplished through one of the following mechanisms: a) the COG screening protocol, b) an IRB-approved institutional screening protocol or c) the study-specific protocol. Documentation of the informed consent for screening will be maintained in the patient's research chart. Studies or procedures that were performed for clinical indications (not exclusively to determine eligibility) may be used for baseline values even if the studies were done before informed consent was obtained.

### **3.7 Eligibility Checklist**

Before the patient can be enrolled, the responsible institutional investigator must sign and date the completed eligibility checklist. A signed copy of the checklist will be uploaded

THIS PROTOCOL IS FOR RESEARCH PURPOSES ONLY, SEE PAGE 1 FOR USAGE POLICY

into RAVE immediately following enrollment.

### 3.8 Institutional Pathology Report

Immediately following enrollment, the institutional pathology report for the diagnosis under which the patient is being enrolled must be uploaded into RAVE. Note: See [Section 4.1.3](#) for exceptions.

The report must include the associated study number and COG patient registration and accession numbers. Personal identifiers, including the patient's name and initials must be removed from the institutional pathology report prior to submission.

### 3.9 Study Enrollment

Patients may be enrolled on the study once all eligibility requirements for the study have been met. Patients who give informed consent for the protocol in order to undergo screening for eligibility are not considered enrolled and should not be enrolled until the screening is completed and they are determined to meet all eligibility criteria. Study enrollment is accomplished by going to the CTSU OPEN (Oncology Patient Enrollment Network) <https://open.ctsu.org/open/>. For questions, please contact the ADV1414 COG Study Assigned Research Coordinator, or the CTSU OPEN helpdesk at <https://www.ctsu.org/CTSUContact.aspx>. Patients must be enrolled before treatment begins. The date protocol therapy is projected to start must be no later than five (5) calendar days after the date of study enrollment. **Patients must not receive any protocol therapy prior to enrollment.**

### 3.10 Dose Assignment

The dose level will be assigned via OPEN at the time of study enrollment.

## 4.0 PATIENT ELIGIBILITY

All clinical and laboratory studies to determine eligibility must be performed within 7 days prior to enrollment unless otherwise indicated. Laboratory values used to assess eligibility must be no older than seven (7) days at the start of therapy. Laboratory tests need **not** be repeated if therapy starts **within** seven (7) days of obtaining labs to assess eligibility. If a post-enrollment lab value is outside the limits of eligibility, or laboratory values are older than 7 days, then the following laboratory evaluations must be re-checked within 48 hours prior to initiating therapy: CBC with differential, bilirubin, ALT (SGPT) and serum creatinine. If the recheck is outside the limits of eligibility, the patient may not receive protocol therapy and will be considered off protocol therapy. Imaging studies must be obtained within 14 days prior to start of protocol therapy (repeat the tumor imaging if necessary).

Clarification in timing when counting days: As an example, please note that if the patient's last day of prior therapy is September 1st, and the protocol requires waiting at least 7 days for that type of prior therapy, then that patient cannot be enrolled until September 8th.

**Important note: The eligibility criteria listed below are interpreted literally and cannot be waived (per COG policy posted 5/11/01). All clinical and laboratory data required for determining eligibility of a patient enrolled on this trial must be available in the patient's medical or research record which will serve as the source document for verification at the time of audit.**

## 4.1 Inclusion Criteria

- 4.1.1 Age: Patients must be  $\geq$  than 12 months and  $\leq$  21 years of age at the time of study enrollment.
- 4.1.2 BSA: Patients must have a BSA  $\geq$  0.84 m^2.
- 4.1.3 Diagnosis:
- 4.1.3.1 Part A: Patients with recurrent or refractory solid tumors, including lymphoma and CNS tumors, are eligible. Patients must have had histologic verification of malignancy at original diagnosis or relapse except in patients with intrinsic brain stem tumors, optic pathway gliomas, or patients with pineal tumors and elevations of CSF or serum tumor markers including alpha-fetoprotein or beta-HCG.
- 4.1.3.2 Part B: Patients with recurrent or refractory high grade glioma (WHO Grade III/IV) including disseminated tumors (excluding DIPG), not requiring surgical resection. Patients must have had histologic verification of malignancy at original diagnosis or relapse.
- 4.1.3.3 Part C: Patients with recurrent or refractory high grade glioma (WHO Grade III/IV) and requiring surgical resection (excluding DIPG and disseminated tumors), who in the opinion of treating physicians, are medically stable to receive 2 doses of selinexor (8-10 days of treatment) before undergoing surgery without compromising the success of the procedure. Note that if, in the opinion of treating physicians, current symptoms necessitate surgery before 2 doses will be able to be received, surgery should not be delayed to administer selinexor, and the patient would be ineligible for protocol therapy.
- 4.1.4 Disease Status:
- Part A: Patients must have either measurable or evaluable disease (see Sections [12.2](#) and [12.3](#) for definitions).
- Parts B & C: Patients must have measurable disease on imaging.
- 4.1.5 Therapeutic Options: Patient's current disease state must be one for which there is no known curative therapy or therapy proven to prolong survival with an acceptable quality of life.
- 4.1.6 Performance Level: Karnofsky  $\geq$  50% for patients  $>$  16 years of age and Lansky  $\geq$  50 for patients  $\leq$  16 years of age (See [Appendix I](#)). Note: Neurologic deficits in patients with CNS tumors must have been relatively stable for at least 7 days prior to study enrollment. Patients who are unable to walk because of paralysis, but who are up in a wheelchair, will be considered ambulatory for the purpose of assessing the performance score.
- 4.1.7 Prior Therapy
- 4.1.7.1 Patients must have fully recovered from the acute toxic effects of all prior

THIS PROTOCOL IS FOR RESEARCH PURPOSES ONLY, SEE PAGE 1 FOR USAGE POLICY

anti-cancer therapy and must meet the following minimum duration from prior anti-cancer directed therapy prior to enrollment. If after the required timeframe, the numerical eligibility criteria are met, e.g. blood count criteria, the patient is considered to have recovered adequately.

- a. Myelosuppressive chemotherapy: At least 21 days after the last dose of myelosuppressive chemotherapy (42 days if prior nitrosourea).
- b. Hematopoietic growth factors: At least 14 days after the last dose of a long-acting growth factor (e.g. Neulasta) or 7 days for short-acting growth factor. For agents that have known adverse events occurring beyond 7 days after administration, this period must be extended beyond the time during which adverse events are known to occur. The duration of this interval must be discussed with the study chair.
- c. Biologic (anti-neoplastic agent): At least 7 days after the last dose of a biologic agent. For agents that have known adverse events occurring beyond 7 days after administration, this period must be extended beyond the time during which adverse events are known to occur. The duration of this interval must be discussed with the study chair.
- d. Immunotherapy: At least 42 days after the completion of any type of immunotherapy, e.g. tumor vaccines.
- e. Antibodies:  $\geq 21$  days must have elapsed from infusion of last dose of antibody, and toxicity related to prior antibody therapy must be recovered to Grade  $\leq 1$
- f. Corticosteroids: See Section 4.2.2.1. If used to modify **immune adverse events** related to prior therapy,  $\geq 14$  days must have elapsed since last dose of corticosteroid.
- g. XRT: At least 14 days after local palliative XRT (small port); At least 150 days must have elapsed if prior TBI, craniospinal XRT or if  $\geq 50\%$  radiation of pelvis; At least 42 days must have elapsed if other substantial BM radiation.
- h. Stem Cell Infusion without TBI: No evidence of active graft vs. host disease and at least 56 days must have elapsed after transplant or stem cell infusion.
- i. Patients must not have received prior exposure to selinexor.

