Accrual to Parts B and C will only open once the MTD or recommended phase 2 dose has been determined in Part A, and may open concurrently with the PK expansion described above.

A maximum of 24 patients are expected to enroll in Parts B and C combined, assuming an inevaluability rate of 20%. We anticipate that each part of the study will require 6-12 months for enrollment.

Response for Part B will be defined as either MR, PR or CR on two consecutive 2D measurements on standard imaging done 4 weeks apart (See [Section 12.6](#)). Sustained responses are very rare in this cohort of recurrent non-DIPG HGGs. We will consider the agent of sufficient interest for further evaluation in this disease category if at least one PR or CR, or at least two MRs, is observed among 10 enrolled patients. A response rate of 20% or more would be evidence of sufficient activity. If the true response rate is 20%, then the probability of observing one or more responses among 10 evaluable patients is about 89.3%. If the response rate is 5%, then the probability of observing at least one response is about 40.1%.

Clinical benefit for Part C will be evaluated separately using the criteria of no visible disease progression six months from the start of treatment. If two or more of a cohort of up to six patients are unable to resume therapy within 6 weeks after surgery, the surgical arm will be declared not feasible. If Part B has fully accrued, Part C will close to further accrual.

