### 12.2.2 Disease Parameters

12.2.2.1 Measurable disease: Measurable lesions are defined as those that can be accurately measured in at least one dimension (longest diameter to be recorded) as  $\geq 20$  mm by chest x-ray, as  $\geq 10$  mm with CT scan, or  $\geq 10$  mm with calipers by clinical exam. All tumor measurements must be recorded in millimeters (or decimal fractions of centimeters).

Note: Tumor lesions that are situated in a previously irradiated area might or might not be considered measurable. If the investigator thinks it appropriate to include them, the conditions under which such lesions should be considered must be defined in the protocol.

12.2.2.2 Malignant lymph nodes: To be considered pathologically enlarged and measurable, a lymph node must be  $\geq 15$  mm in short axis when assessed by CT scan (CT scan slice thickness no greater than 5 mm). At baseline and in follow-up, only the short axis will be measured and followed.

12.2.2.3 Non-measurable disease: All other lesions (or sites of disease), including small lesions (longest diameter  $< 10$  mm or pathological lymph nodes with  $\geq 10$  to  $< 15$  mm short axis), are considered non-measurable disease. Bone lesions, leptomeningeal disease, ascites, pleural/pericardial effusions, lymphangitis cutis/pulmonitis,

THIS PROTOCOL IS FOR RESEARCH PURPOSES ONLY, SEE PAGE 1 FOR USAGE POLICY

inflammatory breast disease, and abdominal masses (not followed by CT or MRI), are considered as non-measurable.

Note: Cystic lesions that meet the criteria for radiographically defined simple cysts should not be considered as malignant lesions (neither measurable nor non-measurable) since they are, by definition, simple cysts. 'Cystic lesions' thought to represent cystic metastases can be considered as measurable lesions, if they meet the definition of measurability described above. However, if non-cystic lesions are present in the same patient, these are preferred for selection as target lesions.

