### 12.6 **Response Criteria for Patients with CNS Tumors**

#### 12.6.1 Measurable Disease

Any lesion that is at minimum 10 mm in one dimension on standard MRI or CT, for CNS tumors.

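### Section 12.6 sets no condition on prior radiation for CNS target lesions, so lasting radiation shrinkage could supply the one PR or CR that meets the Part B rule

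*Combined protocol and SAP*

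**What the plan says.** **Radiation washouts (Section 4.1.7.1.g).** Local palliative radiation has "At least 14 days after local palliative XRT (small port"). The other classes are TBI, craniospinal or extensive pelvic radiation (150 days), and "At least 42 days must have elapsed if other substantial BM radiation". Focal brain radiation that is neither palliative nor craniospinal is not named.

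**Disease status and baseline (Sections 4.1.4 and 4.0).** "Parts B & C: Patients must have measurable disease on imaging". The diagnosis must be recurrent or refractory high-grade glioma. "Imaging studies must be obtained within 14 days prior to start of protocol therapy".

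**CNS response (Section 12.6).** Measurable disease is "Any lesion that is at minimum 10 mm in one dimension on standard MRI or CT, for CNS tumors". Section 12.6.3 selects target lesions by size and by how reliably they can be remeasured. PR is a fall of at least 50% in the summed products of diameters from baseline (12.6.4).

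**Irradiated lesions elsewhere.** Section 12.2.2.1 (RECIST) says that if the investigator wants to use such lesions, "the conditions under which such lesions should be considered must be defined in the protocol". No section defines those conditions. Section 12.4.1 (MIBG) requires a biopsy showing viable tumor, at least 28 days after radiation, when the only positive lesion was irradiated.

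**Part B rule (Section 11.1).** Selinexor is judged worth further study "if at least one PR or CR, or at least two MRs, is observed among 10 enrolled patients". Response must be seen on two consecutive scans 4 weeks apart. Section 11.2.3 counts CR or PR confirmed by central review. Part A patients who meet Part B eligibility and are evaluable for response also enter the rule.

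**The concern.** A lesion that was irradiated shortly before baseline may go on shrinking because of the radiation. If it is the target lesion, Section 12.6 scores that shrinkage as response to selinexor. In a ten-patient cohort where one PR or CR decides the matter, one misattributed response settles the rule.

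The protocol deals with closely related problems elsewhere. It asks for conditions on irradiated lesions under RECIST and requires biopsy proof for a sole irradiated MIBG lesion. It also bars concurrent radiation (Section 7.1) and guards against surgical removal of the tumor before a response is confirmed (Section 11.2.3). The CNS criteria, which govern the only numeric activity rule in the trial, have no matching provision.

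**Working it through.** **1. Can a recently irradiated lesion be a baseline target?** Take local palliative radiation ending on day 0. Enrollment is possible from day 14, and therapy may start that day. The baseline scan may be up to 14 days before therapy, so the earliest scan is day 14 − 14 = day 0. The baseline cannot precede the end of that radiation, but it can fall on its last day, before later shrinkage. For other focal brain radiation the documents name no class, so no such bound can be derived.

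**2. Does another rule close the gap?**

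| Rule | What it does | What it leaves open |
|---|---|---|
| Recurrent or refractory disease (4.1.3.2) | Requires failure of earlier therapy | Does not require the target lesion to have progressed after its last radiation |
| Two scans 4 weeks apart (11.1) | Removes transient change | Lasting radiation shrinkage passes |
| Central review (8.2.1, 11.2.3) | Confirms the response | Not stated to consider radiation date or field |
| RECIST note (12.2.2.1) | Calls for conditions | None defined; does not govern CNS scoring |
| MIBG biopsy (12.4.1) | Requires viable tumor | Neuroblastoma only |

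**3. The plan's own figures.** With n = 10 and a rule of at least one response, P(go) = 1 − (1 − p)^10.

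- p = 0.20: 1 − 0.80^10 = 0.8926 (stated 89.3%).
- p = 0.05: 1 − 0.95^10 = 0.4013 (stated 40.1%).

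Both reproduce.

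**4. Illustration of size.** Let k of the ten patients have a recently irradiated target lesion, and let q be the chance that radiation alone gives such a patient a confirmed PR. The documents give neither k nor q; both are assumptions. Treating patients and causes as independent, and ignoring the route through two MRs:

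P(go) = 1 − (1 − p)^10 × (1 − q)^k, with p = 0.05 and 0.95^10 = 0.5987.

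For k = 1 and q = 0.10: 1 − 0.5987 × 0.90 = 0.461. For k = 1 and q = 0.30: 1 − 0.5987 × 0.70 = 0.581.

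| k | q = 0.10 | q = 0.20 | q = 0.30 |
|---|---|---|---|
| 0 | 40.1% | 40.1% | 40.1% |
| 1 | 46.1% | 52.1% | 58.1% |
| 2 | 51.5% | 61.7% | 70.7% |
| 3 | 56.4% | 69.3% | 79.5% |

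For a drug with no activity (p = 0), the chance of a go is q itself when k = 1, that is 10% to 30% instead of 0%.

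**The case against.** The strongest reply is that the protocol already holds several safeguards and that little hangs on the result. Disease must be recurrent or refractory. For palliative radiation the baseline scan cannot predate the end of treatment. PR needs a 50% fall that lasts to a second scan, and central review must agree. MR also requires stable or decreasing steroids and a stable or improving neurologic examination. A go means only that further evaluation is of interest, antitumor effect is a secondary aim, and Section 11.5 calls the analyses descriptive and exploratory. The plan openly accepts a 40.1% chance of a go at a 5% rate. All of this stands. It lowers the likelihood and the stakes, but none of it separates lasting radiation shrinkage from drug effect.

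Two points on size also stand. Section 11.1 calls 5% simply the response rate, so adding a radiation component may double-count; it also says that sustained responses are very rare in this population. And the bias can run the other way, because post-radiation swelling that grows after baseline would be scored as PD at a 25% increase.

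Three stronger readings are tempting, and the documents do not support them:

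- *Any glioma lesion may be irradiated up to 14 days before enrollment.* That interval covers local palliative small-port radiation only. Craniospinal radiation needs 150 days, which matters because Part B admits disseminated tumors.
- *The note in Section 12.2.2.1 is a broken promise for Part B.* It is conditional and sits in the RECIST section; Part B is scored under 12.6.
- *Part C has the same flaw.* Its outcome is absence of visible progression at six months, so the single-PR route does not apply.

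**Conclusion.** The gap in Section 12.6 is real and worth correcting, but modest. Following the plan as written, lasting shrinkage of an irradiated target lesion can count as the one PR or CR that meets the Part B rule, whether the patient came through Part B or was brought in from Part A. For RECIST patients in Part A the effect is confined to descriptive reporting, although there the protocol's own call for conditions is unmet.

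The size cannot be estimated from the documents. As an illustration, one affected patient with an assumed 10% to 30% chance of a radiation-only confirmed PR moves the chance of a go at a 5% rate from 40.1% to about 46% to 58%. This assumes that the 5% excludes any radiation effect and that the bias runs only toward response. A reader might infer that radiation is known to inflate the rule by this much, or that central review could not catch it. Neither follows: the rates are assumed, and the protocol does not say what the central reviewers consider.

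**What to change.** 1. In Sections 12.6.1 and 12.6.3, state that a lesion in a previously irradiated field may be a target lesion for response only if progression in that lesion was documented on imaging after that radiation ended. Put the same condition in Section 12.2.2.1, which already calls for one.
2. Record the date and field of last radiation for every patient who enters the Part B rule, including those from Part A.
3. List the interval from last radiation to the baseline scan for every responder.
4. Report the Part B rule with and without responses in recently irradiated target lesions, with the sponsor fixing the meaning of recently before the results are read.

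The washout intervals in Section 4.1.7.1.g and the Part C criteria need no change for this purpose, and the wording should be limited to target lesions for response so that Part C eligibility is untouched. A fixed waiting period after radiation is not proposed, because the documents contain no figure to support one.

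The cost is a few sentences, two data items that sites should already hold, and one extra listing. The downside is that a few Part B candidates may lack a qualifying target lesion.
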